We will conduct a retrospective chart review to explore social determinant of health barriers to vaccine series completion from a retrospective chart review of patients who initiated but did not complete the HPV vaccine series during our study. We will identify patients within the cohort at PPCC and Hopple who initiated but did not complete the HPV vaccine series within a 14 month period following a visit with physicians that participated in the Aim 2 portion of the study. For patients under the age of 15 years, the second dose of the HPV vaccine series is to be administered six months following the first dose. We have operationalized HPV vaccine series completion to occur within 14 months as this provides an adequate and pragmatic timeframe for vaccine series completion at a follow-up visit or annual well child visit.

The primary outcome is the proportion of patients within a cohort at PPCC and Hopple who initiated but did not complete the HPV vaccine series within a 14 month period following a visit with physicians that participated in the Aim 2 portion of the study. These data will be obtained from the EPIC electronic medical record of patients who initiated the HPV vaccine series but have yet to complete it. Data will be entered into a REDCap database. The research materials to be obtained from participants are data collected through review of retrospective chart review of the GPC Social Risk Family Questionnaire, demographic data (DOB, age, sex, race, ethnicity, health insurance), visit information, and HPV vaccine dates (see appendix VICTORI Chart Review).

Potential Benefits

Providers who participate in the VICTORI curriculum will obtain additional knowledge on how to appropriately counsel parents that express vaccine hesitancy. The goal is to improve physician-patient communication which results in improved clinical outcomes (less vaccination refusal) for this high-risk population.

Potential Risks

Aim 1: Evaluate VICTORI for acceptability and feasibility

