anticipate the findings to be generalizable to other urban primary care clinics that serve predominantly minority populations. The PPCC is staffed by approximately 20 attending physicians (total: 8.0 Full-time equivalent), 80 pediatric residents, 25 nurses, 21 medical assistants, 5 nurse care managers, 3 social work care managers, 3 social workers, 1 community engagement specialist, 14 community health workers, 2 customer service representatives, and 6 psychologists. Additionally, we will recruit resident and attending physicians from the HSNHC who will not receive the VR intervention but will serve as controls, only receiving the self-directed app-based curriculum. HSNHC serves a predominantly underserved population as well with 90% publicly insured. Seventy-three percent of the patient population is African American, and 5% is Latino. HSNHC is staffed by approximately 7 attending physicians (total: 2.5 Full-time equivalent) and 28 pediatric residents. HPV initiation rates in Ohio are 57% for girls and 55% for boys; completion rates are 42% for girls and 41% for boys.¹ The completion rate in Hamilton County is 16% for boys and girls combined.⁶⁸ The vaccination initiation rates in the PPCC (FY17) for 11 to 12-year-old girls was 48% (257 vaccinations initiated out of 537 visits) and for 11 to 12-year-old boys was 52% (289 vaccinations initiated out of 557 visits). The HPV vaccination initiation rate in the PPCC (FY17) for 11 to 17-year-old boys and girls was 43% (619 vaccinations initiated out of 1450 visits). The rationale for including adolescents 9 to 17 years old is this will allow us to perform a stratified analysis to determine if the intervention is more effective during the target range (11-12 years), the catch-up range (13-17 years), or early vaccination range (9-10 years). In addition, the National Immunization Survey (NIS) for Teens assesses vaccination rates in children age 13-17 years. By including all children age 9-17 years within our study population, it will allow comparison with the NIS-Teen outcome measures. The PPCC cares for very few patients 18 years and older, and we therefore did not extend our population beyond 17 years. HSNHC, environmental control, had a 51% HPV initiation rate (FY17) for 11 to 17-year-old boys and girls (183 vaccinations out of 357 visits). The HSNHC serves a comparable site to the PPCC and is similarly staffed by physicians from CCHMC though distinct from those physicians practicing at PPCC.

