Setting and Population: The PPCC is a busy, academic clinic in Hamilton County, Ohio with about 33,000 visits annually, serving 19,000 patients that are predominantly underserved with approximately 90% insured through Medicaid. Seventy-five percent of the patient population is African American and 5% is Latino. PPCC serves a population that is at high risk for HPV infection and its sequela, and therefore, we anticipate the findings to be generalizable to other urban primary care clinics that serve predominantly minority populations. Hopple Street Neighborhood Health Center (HSNHC) which served as a control during Aim 2, serves a similar population to the PPCC with 6000 unique patients and 13,000 patient visits per a year.

Design and Measures: We will first identify patients aged 9 to 17-year-old boys and girls who initiated the HPV vaccine series between 10/01/2020-06/01/2022 after seeing a provider who underwent VICTORI training. We will review social determinants of health screener of those who had not completed the HPV vaccine series by 14 months after initiation compared to those who did complete the HPV vaccine series. We will also collect demographic information (DOB, age, sex, race, ethnicity, health insurance; see appendix VICTORI Chart Review),

Based on these data, future revisions will be made to VICTORI to allow physicians to deliberately practice screening for and addressing barriers to vaccine series completion. Findings from this aim will provide

information to create a data-informed enhancement of VICTORI's simulated scenarios supporting series completion, which is critical to decreasing morbidity related to HPV-associated cancers.

Data Analysis and Sample Size Calculations:

- Review between n = 300 (minimum) – 720 (maximum) patient records

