- These sample size calculations were derived from Peduzzi et al. {Peduzzi, 1996 #3012} guideline for the minimum number of cases to include for a logistic regression. The formula used for the calculation of the minimum number of participants was $N = 10 * 18 \text{ variables} / 60\%$ (the estimated proportion of patients who completed the HPV vaccine series). The formula used for the calculation of the maximum number of participants was $N = 10 * 18 \text{ variables} / 25\%$ (the estimated proportion of patients who completed the HPV vaccine within the recommended timeframe). As a note, we will also examine the proportion of patients who meet the guidelines for timely series completion (N = 400 minimum) using the following equation: $N = 10 * 18 \text{ variables} / 45\%$ (the estimated proportion of people who completed the HPV vaccine within the recommended timeframe).
- Descriptive analyses as well as data variance and distribution to characterize variables.
- Logistic regression to determine factors independently associated with completing the HPV vaccine series including: clinic location (PPC v Hopple), type of visits at first dose, resident v attending physician, provider sex, age of patient at first dose, patient sex, patient race, insurance at first dose, and social risk screener questions.

Required dose for vaccine series completion (2 doses v 3 doses) will also be included in the descriptive analyses

Training of Study Personnel

All staff will undergo training in maintaining confidentiality and have completed the required Collaborative Institutional Training Initiative (CITI) courses and research ethics classes as required by CCHMC and Cincinnati Children's Research Foundation.

Recruitment and Consent Procedure

Aim 1: Evaluate VICTORI for acceptability and feasibility

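### Aim 3's fixed 14-month completion window may outlast observation for PPCC patients who start after 16 years 10 months; the effect is small and falls mainly on the age coefficient

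*Combined protocol and SAP*

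**What the plan says.** **Cohort.** Aim 3, Design and Measures: "We will first identify patients aged 9 to 17-year-old boys and girls who initiated the HPV vaccine series between 10/01/2020-06/01/2022". The only age rule applies at entry.

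**Outcome.** The same section compares patients who finished with "those who had not completed the HPV vaccine series by 14 months after initiation". Protection of Subjects, Aim 3, sets one window for all ages: "We have operationalized HPV vaccine series completion to occur within 14 months". It justifies this length by the chance to finish at a follow-up or yearly well-child visit, and it discusses dose timing only for patients under 15.

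**Source and sites.** The same section names both clinics ("We will identify patients within the cohort at PPCC and Hopple who initiated but did not complete the HPV vaccine series within a 14 month") and the data source: "These data will be obtained from the EPIC electronic medical record of patients who initiated the HPV vaccine series".

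**Retention.** Aim 2, Setting and Population, explains the age cap: "The PPCC cares for very few patients 18 years and older, and we therefore did not extend our population beyond 17 years". Nothing comparable is said of HSNHC.

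**Model.** Aim 3, Data Analysis and Sample Size Calculations, lists among the logistic regression covariates "age of patient at first dose, patient sex, patient race, insurance at first dose, and social risk screener questions".

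None of these sections sets an upper age at first dose that leaves 14 months before 18, requires continued care, gives a transfer or censoring rule, or says whether doses given elsewhere are captured.

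**The concern.** The cap at 17 controls who enters. It does not secure the follow-up that the outcome needs. For a patient who starts at 17 or later, the next yearly visit falls on or after the 18th birthday, when by the plan's own account few patients are still at the PPCC. The reason given for 14 months is therefore weakest in this group.

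With a yes/no outcome, a patient who has left and a patient who stayed but did not return look the same: neither has a recorded last dose. Aim 3 exists to find barriers to completion, and age at first dose is in the model. Ageing out of the clinic could appear there as lower completion at older ages. Adjusting for age does not repair an outcome that has been misclassified, and a straight-line age term cannot follow a change confined to the last 14 months before 18.

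**Working it through.** **Plan's own figures.** Aim 3 sizes the review as 10 × 18 / p. With p = 0.60, 0.25 and 0.45 this gives 300, 720 and 400, as stated. Nothing below changes these numbers.

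**Age cut-off.** 18 years − 14 months = 216 − 14 = 202 months = 16 years 10 months.

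**Share of initiators above the cut-off.** The FY17 PPCC counts are in Aim 2, Setting and Population.
- Ages 11-12: 257 + 289 = 546 initiations.
- Ages 11-17: 619. Ages 13-17: 619 − 546 = 73.
- Assuming the 73 are spread evenly over 60 months: (73/619) × (14/60) = 2.8%.
- Charts: 8 of 300, 11 of 400, 20 of 720.
- Range: 0% to 73/619 = 11.8%, the upper end if every 13-17-year-old initiator were past the cut-off.

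The FY17 counts omit ages 9-10, and the documents give no figure for them. If 100, 273 or 546 initiations at 9-10 are assumed, the share falls to 2.4%, 1.9% or 1.5%.

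**Effect on completion.** Assume true completion of 60% at every age (the plan's sizing figure), that all patients leave at 18, and that later doses are not seen. Follow-up is f = min(14, months to the 18th birthday). Two timing patterns are assumed for completions:
- spread over months 6-14: observed completion = 0.6 × (f − 6)/8, bounded at 0 and 0.6;
- spread over months 6-8: observed completion = 0.6 × (f − 6)/2, bounded likewise.

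Averaging over f from 0 to 14 gives, among patients past the cut-off:
- months 6-14: 0.6 × 4/14 = 17%;
- months 6-8: 0.6 × 7/14 = 30%.

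The fall in overall completion is 2.75% × (60 − 17.1) = 1.2 points, or 2.75% × (60 − 30) = 0.8 points. That is 5.9 to 8.5 missed completions in 720 charts, or 2.5 to 3.5 in 300. If every would-be completer past the cut-off were missed, the fall would be 2.75% × 60 = 1.7 points, or 7.1 points at the 11.8% upper bound.

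**Effect on the age coefficient.** A logistic regression of this observed completion on age in years, weighted 546 (ages 11-12) and 73 (ages 13-17), when the true odds ratio is 1:

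| Assumption | OR per year | z at 720 | z at 400 | z at 300 |
|---|---|---|---|---|
| All leave, months 6-14 | 0.87 | −2.43 | −1.81 | −1.57 |
| All leave, months 6-8 | 0.91 | −1.76 | −1.31 | −1.14 |
| Half leave, months 6-14 | 0.93 | −1.23 | −0.92 | −0.79 |
| Half leave, months 6-8 | 0.95 | −0.89 | −0.66 | −0.57 |

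If ages 9-10 are added under full departure, z at 720 weakens from −2.43 to −1.99 (100 initiations), −1.63 (273) or −1.34 (546).

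Limiting the same model to first doses before 16 years 10 months returns an odds ratio of 1.00 and completion of 60%.

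**The case against.** The strongest reply is that loss of observation is inferred. The plan says very few PPCC patients are 18 or older. It does not say that patients leave on their birthday. The source is described as the Epic record, not one clinic's part of it, and doses given later or elsewhere may appear there. HSNHC is in the cohort and no such statement is made about it. All of this stands: a later dose *may* not be seen, and that is as far as the text goes.

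A reader might infer that everyone who starts after 16 years 10 months is scored as a non-completer. That is not so. Anyone who finishes before leaving is scored correctly, a patient starting at exactly 17 still has 12 months before 18, and under even ages only half of the affected group's window falls after 18.

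A reader might also infer that the artefact would misdirect the revision of VICTORI. The documents do not support that. The revision is to rest on barriers to completion, with the social determinants screener as the main comparison. Age at first dose is not modifiable, and as a covariate it would take up part of the artefact. No distortion of a screener item has been shown. A shift in the clinic-location coefficient is possible if the two clinics keep 18-year-olds differently, but the documents are silent on this.

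What the reply does not remove is the gap itself: the plan has no rule that separates not completing from no longer being observed.

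**Conclusion.** The point holds in a limited form. For PPCC patients whose first dose falls after 16 years 10 months, the 14-month outcome may mix non-completion with departure from the clinic. This touches about 2-3% of charts and moves overall completion by about 1 point. The effect falls mainly on the age coefficient, and the false odds ratio reaches nominal significance only near 720 charts with full departure at 18.

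These sizes rest on the FY17 age mix, even ages within 13-17, 60% completion at every age, the two assumed timing patterns, and applying the PPCC statement to the whole cohort. Including ages 9-10, partial departure, or capture of outside doses in Epic would shrink them. An older initiator mix than in FY17 would enlarge them. It is a cheap improvement, not a threat to Aim 3's main comparison.

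**What to change.** In Aim 3, Design and Measures and Data Analysis, take one of two routes.

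1. Run the 14-month completion proportion and the logistic regression in patients whose first dose was given at least 14 months before their 18th birthday. Make this the main analysis, or at least a prespecified sensitivity analysis, and describe older initiators separately.
2. Keep all patients and analyse time to completion, censoring at last recorded contact. Censoring at the 18th birthday would impose an exit date that the documents do not give and would discard doses recorded afterwards. Last-contact censoring has its own weakness: not returning is part of what Aim 3 studies, so censoring may be informative. The first route is simpler for that reason.

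Under either route, state whether Epic captures doses given outside the two clinics, and whether HSNHC keeps patients past 18.

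The cost is a few lines of text. Date of birth, visit information and dose dates are already to be extracted. The first route loses about 3% of charts and gives no 14-month completion estimate for the oldest initiators in the restricted analysis.

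### The Aim 3 minimum of 300 charts is sized on the 60% who complete the series; the 40% who do not are the limiting group, and 10 per variable needs 450

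*Combined protocol and SAP*

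**What the plan says.** The sample size for the Aim 3 chart review is in the combined protocol and SAP, Aim 3, Data Analysis and Sample Size Calculations. The range is "Review between n = 300 (minimum) – 720 (maximum) patient records". Its only stated basis is a published "guideline for the minimum number of cases to include for a logistic regression", applied as 10 per variable with 18 variables. No effect size, power or significance level enters.

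Three numbers come from the same formula with different divisors:

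- **300, the minimum:** divisor 60%, described as "the estimated proportion of patients who completed the HPV vaccine series".
- **720, the maximum:** divisor 25%, described as "the estimated proportion of patients who completed the HPV vaccine within the recommended timeframe".
- **400, a minimum for an additional look at timely completion:** divisor 45%, described as "the estimated proportion of people who completed the HPV vaccine within the recommended timeframe".

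The planned model is given as "Logistic regression to determine factors independently associated with completing the HPV vaccine series including" eight named covariates and the social risk screener questions. Under Aim 3, Design and Measures, patients not complete by 14 months after initiation are compared with those who did complete. The title of Aim 3 refers to non-completion, and under Protection of Subjects its primary outcome is the proportion who started the series but did not finish it within 14 months.

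**The concern.** The formula divides by the proportion who completed, whatever that proportion is. This does no harm while completers are the smaller group, as at 25% and 45%. At 60% they are the larger group, and the formula then counts the outcome that is in good supply.

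Swapping the coding of a binary outcome reverses the signs of the logistic coefficients and leaves their standard errors unchanged. The number of charts needed therefore cannot depend on which outcome is called the case. Yet the plan's formula gives 300 if the event is completion and 450 if it is non-completion, for the same model on the same charts. The group left short is the one Aim 3 is about.

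At stake is the precision of the odds ratios, above all those for the social risk items that are to guide later revisions of VICTORI.

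A second problem sits beside the first. Two consecutive sentences give 25% and 45% for what reads as the same quantity, and these imply different chart numbers. A reader cannot tell whether 400 charts are enough for the timely-completion analysis.

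**Working it through.** **Inputs.** From the plan: 10 per variable; 18 variables; 60% completing the series; 25% and 45% for timely completion; 300, 400 and 720 charts. Derived: 1 − 0.60 = 0.40 not completing.

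**1. The plan's figures reproduce.** With N = 10 × 18 / p:

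- 180/0.60 = 300
- 180/0.25 = 720
- 180/0.45 = 400

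**2. Outcome coding.** An 18-predictor logistic model was fitted to 300 simulated records, once for completion and once for non-completion. The coefficients changed sign only, and the standard errors agreed to rounding error. The smaller group is therefore the one to count.

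**3. Corrected formula.** With N = 180 / min(p, 1 − p):

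- Series completion: 180/0.40 = 450
- Timely completion at 25%: 720, unchanged
- Timely completion at 45%: 400, unchanged

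**4. Non-completers per variable, if 60% complete.**

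| Charts | Non-completers | Per variable (÷ 18) |
|---|---|---|
| 300 | 120 | 6.7 |
| 400 | 160 | 8.9 |
| 450 | 180 | 10.0 |
| 720 | 288 | 16.0 |

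**5. Dependence on the 60%.** The required number is 180/0.45 = 400 at 55% completing, 180/0.35 = 515 (rounded up) at 65%, and 180/0.30 = 600 at 70%. The most favourable case is an even split, which needs 180/0.50 = 360. So no completion proportion makes 300 charts enough for 18 variables at 10 each.

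**6. Direction of the printed formula.** Above 50% it asks for fewer charts as non-completers become scarcer. At 75% completing (a value chosen only to show this) it gives 180/0.75 = 240 charts with 60 non-completers, or 60/18 = 3.3 per variable. The corrected formula gives 180/0.25 = 720.

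**7. Timely completion at 400 charts.** At 45%, 400 × 0.45/18 = 10.0 per variable. At 25%, 400 × 0.25/18 = 5.6.

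**8. Effect on precision.** This is an illustrative simulation. The assumptions are not in the plan, apart from the 18 predictors and the 40% non-completion its estimate implies: independent binary predictors, each with 20% prevalence, one with a true odds ratio of 1.5; 2,000 replicates per size.

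| Charts | Mean SE of log OR | Typical 95% CI around 1.5 | Coverage |
|---|---|---|---|
| 300 | 0.313 | 0.81–2.77 | 94.7% |
| 400 | 0.266 | 0.89–2.53 | 95.2% |
| 450 | 0.249 | 0.92–2.44 | 94.7% |
| 720 | 0.193 | 1.03–2.19 | 95.2% |

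There were no fitting failures. A typical interval is exp(ln 1.5 ± 1.96 × SE).

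**The case against.** The plan's three sums are exact and follow one convention: count the outcome being modelled. On that reading 300 charts supply 180 completers, which is 10 per variable. The plan does not itself say that cases means the rarer outcome, and the cited guideline is not among the documents.

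The 6.7 is also the worst case. Charts may run to 720, 450 is already inside the range, and if the 400 minimum for timely completion governs the same charts (which is not stated) the figure is 8.9.

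Ten per variable is a rule of thumb, and the simulation shows sound coverage at 300. Most of the gain at 450 is simply the larger sample: 0.313 × √(300/450) = 0.256, against 0.249 simulated, so about 90% of the reduction in standard error. The interval at 450 still includes 1. The 450 rests on a 60% estimate that the plan does not tie to the 14-month window. Finally, 25% and 45% may be a low and a high estimate, since one sets a maximum and the other a minimum.

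Much of this stands as a limit on importance. The aim is exploratory, a 300-chart model would not be invalid, and 450 is conditional on the 60%. The defence of the convention does not stand: the same model cannot need 300 charts under one coding and 450 under the other. Uncertainty about the 60% does not rescue 300 either, since even an even split needs 360. The low-and-high reading of 25% and 45% is plausible, but the plan does not say so.

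**Conclusion.** The minimum of 300 is wrong as written. On the plan's own inputs it gives 6.7 non-completers per variable, and the 10 per variable it is built on needs 450 charts. The 720 and 400 figures do not change under the same correction.

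This rests on three things: the plan's 60% estimate applying to the outcome analysed, 18 being the number of model parameters, and the plan's own choice of 10 per variable. If some of the 18 are multi-level factors, the required number is higher.

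The consequence is wider confidence intervals at the stated minimum, confined to Aim 3, and it disappears if at least 450 charts are reviewed. The 25% and 45% need reconciling as a separate matter. The point should be fixed, but it does not touch the Aim 2 primary analysis.

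**What to change.** 1. Replace the divisor by the smaller of p and 1 − p, and restate the series-completion minimum as 180/0.40 = 450. State whether the 60% refers to completion by 14 months, and restate the number if that estimate changes.
2. Say whether 18 counts variables or parameters. Each level beyond the reference for visit type, race and insurance is a parameter. If the count rises, so does the minimum.
3. For timely completion, settle on one estimate, or label 25% and 45% as different quantities or as a low and a high estimate, and give the matching number of charts.

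The cost is low. The review is retrospective and already allows 720 charts, so the change is at most 150 more than the current minimum (450 − 300) plus a few lines of text.

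The alternative is to keep 300 charts and limit the model to 120/10 = 12 parameters, or 160/10 = 16 with 400 charts. This needs no extra charts, but 12 parameters means giving up a third of the 18, possibly including social risk items. Raising the minimum is the better choice. If the model is cut instead, the retained parameters should be fixed before the outcome data are examined.

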
Data Analysis: Repeated measures generalized linear mixed-effects regression (GLMER) will be used to test whether vaccine initiation and completion rates of 9 to 17-year-old boys and girls increase in response to VICTORI. Models will include a logit link function to model the binary patient-level response of vaccine initiation (yes/no) and a random subject-specific intercept to account for patient encounters nested within physicians. Our primary outcome, determining the increase in the proportion of patients receiving HPV vaccination seen by resident and attending physicians in response to the intervention will be tested using the GLMER model including fixed-effect terms for study month (i.e., time) and period (pre-intervention vs. post-intervention). A likelihood ratio test (LRT) for period will provide a formal test of whether vaccine initiations increase in response to the intervention. Differences in the trajectory (i.e., change in slopes) of vaccine initiations between pre- and post-intervention periods will be tested by the inclusion of an interaction term for time and group. The inclusion of a random slope for time will be determined based on assessment of model fit. Polynomial terms or restricted cubic splines will be considered to model non-linear associations in vaccine initiation (i.e., capture the possible early intervention effect and subsequent decline). Additional terms as described for resident and attending physicians in phase I will be added to capture changes in the level and slope of vaccine initiation in response to training staff in phase II. Primary analyses will be conducted for

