determining whether VICTORI increases vaccine initiation. The PPCC is staffed by 80 residents and 20 attending physicians and reflects the maximum sample size for the intervention. To inform our power calculations for this proposal, we reviewed all PPCC patient visits for 11 to 17-year-old boys and girls from July 1, 2016 to June 30, 2017. HPV vaccination was initiated in 53% of visits for residents and 34% for attending physicians with greater between provider variation for residents. In addition, attending physicians saw more patients (n=9) in this age range on average per month than residents (n=2), and graphical analyses and formal regression modeling did not support material seasonal variation in initiation rates. Simulated outcomes based on these data were used to determine the minimum detectable odds ratio (OR) for vaccine initiation according to study period (i.e. pre- vs. post-intervention) as estimated from the proposed GLMER model. For resident and attending physicians combined, we assumed a total of 70 physicians having on average four patient encounters per month, a baseline probability of vaccine initiation of 43%, and a standard deviation for the subject-specific intercept of 0.55. Study power was determined to be 80% to detect an OR=1.5 based on 10k simulations. *This corresponds to a post-intervention vaccine initiation probability of 53%; or a 10% pre- to post-intervention difference.* Thus, conducting this intervention at CCHMC is expected to provide sufficient power to detect a clinically meaningful effect size for the response.

Potential Problems and Alternative Strategies: Insufficient recruitment may occur, but we do not anticipate this to be an issue as we have successfully conducted a VR intervention focused on flu vaccination with this population.²⁶ In addition, our team and expert consultants have provided extensive recommendations to recruit providers. There is the possibility of incomplete surveys; scale items with <25% missing data will be included in the analysis.⁷⁸ Multiple imputation and/or maximum likelihood estimation will be implemented should material missing values be realized for the survey responses and we will conduct a sensitivity analyses to determine the robustness of study findings to the assumptions of the imputation model.

Aim 3: Determine modifiable barriers related to HPV vaccine non-completion for future enhancement of VICTORI accordingly

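### The Aim 3 logistic regression makes no stated allowance for patients nested within physicians, so clinic, resident/attending and provider-sex results will look too precise if completion varies by physician

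*Combined protocol and SAP*

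**What the plan says.** In the combined protocol and SAP, Aim 3, Data Analysis and Sample Size Calculations, the inferential analysis is one bullet: "Logistic regression to determine factors independently associated with completing the HPV vaccine series". The listed factors begin with "clinic location (PPC v Hopple), type of visits at first dose, resident v attending physician, provider sex" and continue with patient characteristics and the social risk screener questions. The sample size is "Review between n = 300 (minimum) – 720 (maximum) patient records", from a ten-per-variable rule described as a "guideline for the minimum number of cases to include for a logistic regression". Neither the model nor the sample size mentions clustering.

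Under Protection of Subjects, Aim 3, the cohort is defined by a visit, at either clinic, with a physician who took part in Aim 2.

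For Aim 2, the Data Analysis section specifies a mixed model with "a random subject-specific intercept to account for patient encounters nested within physicians". It applies that model to completion as well as initiation. Power considerations assumes "a standard deviation for the subject-specific intercept of 0.55", for initiation.

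**The concern.** Patients who share a physician may resemble each other in whether they complete the series. Ordinary logistic regression counts every patient as a separate piece of information. For a factor that does not change within a physician, the information comes largely from the number of physicians, so the model overstates precision whenever completion varies between them. Aim 2 accepts this for completion, and Aim 3 studies patients of the same physicians without carrying it over.

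At stake are the reported intervals and p-values for three of the named factors. Clinic matters most. PPCC physicians receive the app and VR simulations and HSNHC physicians the app alone, so an overstated clinic result could be taken as an effect of VR training on completion.

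**Working it through.** **1. The plan's own figures.** N = 10 × 18 / p gives 180/0.60 = 300, 180/0.25 = 720 and 180/0.45 = 400. All three match the text. None contains a design effect.

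**2. Inputs.**
- Physicians: 70 at PPCC and 35 at HSNHC, total 105 (Protection of Subjects, Aim 2). Both clinics are included because clinic is a listed factor.
- Attendings: 20 of 100 at PPCC and 7 of 35 at HSNHC, so one in five, or 21 of 105. Some simulations used 27 attendings (20 + 7) and 78 residents.
- Volumes: 9 patients per month for attendings and 2 for residents (Power considerations).
- Between-physician SD on the logit scale: 0.55, stated for initiation. Carrying it to completion is an assumption, so 0 to 0.80 was also tried.
- Alpha: two-sided 0.05, assumed, because Aim 3 states none.

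**3. Intraclass correlation at SD 0.55.** On the latent scale, 0.55² / (0.55² + π²/3) = 0.3025 / 3.592 = 0.084. On the observed scale (variance of physician-specific probabilities divided by p(1 − p)) it is 0.064 at 60% completion, 0.066 at 45% and 0.052 at 25%.

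**4. Design effect for a factor constant within physician.** DE = 1 + (m − 1) × ICC. With unequal volumes, m = 1 + (N − 1)Σw², where w is each physician's share of patients. For 21 attendings and 84 residents at 9:2, Σw² = (21×81 + 84×4)/357² = 0.0160. The implied type I error is 2[1 − Φ(1.96/√DE)].

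| N, completion | m | DE | True SE / ordinary SE | Implied type I error |
|---|---|---|---|---|
| 300, 60% | 5.8 | 1.31 | 1.14 | 8.6% |
| 400, 45% | 7.4 | 1.42 | 1.19 | 10.0% |
| 720, 25% | 12.5 | 1.60 | 1.27 | 12.2% |

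Equal volumes (m = N/105) give DE of 1.12, 1.18 and 1.31, hence 6.4%, 7.2% and 8.6%. Aim 3 counts initiators, not visits. Multiplying volumes by the reported initiation rates (9 × 0.34 = 3.06; 2 × 0.53 = 1.06) gives Σw² = 0.0124 and DE of 1.24, 1.32 and 1.47, hence 7.8%, 8.9% and 10.6%.

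**5. Null simulation.** There were 1,500 replicates per setting, 21 attendings and 84 residents, 9:2 volumes and no true effects. The model held clinic, attending status, provider sex and one binary patient-level covariate, not all 18 variables. Each cell gives the range over the three physician- or clinic-level factors.

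| N, completion | SD 0 | SD 0.30 | SD 0.55 | SD 0.80 | SD 0.55, SE clustered, uncorrected |
|---|---|---|---|---|---|
| 300, 60% | 4.5-5.6% | 5.5-6.9% | 9.0-9.7% | 11.6-12.7% | 6.3-7.0% |
| 400, 45% | 4.9-5.2% | 6.1-7.0% | 9.1-11.1% | 13.8-15.9% | 6.5-7.6% |
| 720, 25% | 4.1-5.9% | 6.4-7.8% | 11.5-12.4% | 17.3-19.5% | 6.1-6.8% |
| 720, 60% | 4.4-5.5% | 7.3-8.6% | 12.8-14.5% | 19.0-22.3% | 5.6-6.9% |

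The patient-level covariate stayed at 3.9-5.9% in every setting. With 27 attendings and 78 residents, SD 0.55 gave 8-9%, about 10% and 11-13% at N of 300, 400 and 720.

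**6. A smaller SD that the document's figures also allow.** The Aim 2 primary model lists only month and period as fixed effects, so 0.55 may include the attending/resident gap. That gap is logit(0.53) − logit(0.34) = 0.120 + 0.663 = 0.783. Twenty attendings among 70 physicians reproduce the assumed four encounters per month: (20×9 + 50×2)/70 = 4. The gap then contributes 0.783² × (20/70)(50/70) = 0.125, leaving √(0.3025 − 0.125) = 0.42. Simulation at SD 0.42 (2,000 runs, 27 attendings) gave 6-8% at N=300, 7-8% at N=400 and 8-10% at N=720.

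**The case against.** The strongest reply concerns size. The SD of 0.55 describes initiation. It may already contain the attending/resident difference, for which the Aim 3 model adjusts. The plan also reports more between-provider variation among residents, whereas attendings form the large clusters that drive the inflation. An assumed split of 0.30 for attendings and 0.55 for residents gave 5-7%, 6-8% and 7-9% at the three sample sizes. Completion depends on a later dose, up to 14 months on, which the documents do not say the dose-one physician gives. Its between-physician variation could be smaller or larger. At SD 0.30 and N=300, ordinary and uncorrected clustered tests can hardly be told apart. All of this stands, and it is why a range is given.

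The plan is also silent on clustering rather than opposed to it. That is fair, but an analyst who follows the bullet as written would fit a model without adjustment, and Aim 2 shows that the nesting was recognised.

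A reader might infer that false barriers would be built into the next version of VICTORI. The documents do not support that. The planned revision concerns screening for and addressing barriers to completion. Attending status, provider sex and clinic are not modifiable barriers or screener items. The social-risk items are little affected if they vary within physician.

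**Conclusion.** The omission is real and minor. Given any between-physician variation in completion, the direction is clear: standard errors and p-values for clinic, resident versus attending and provider sex are too small.

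The size rests on assumptions: alpha 0.05, 105 physicians, 9:2 volumes and an SD that the plan does not give for completion. With 0.55, type I error is about 8-10% at N=300, 9-11% at N=400 and 11-15% at N=720. With 0.30 to 0.42 it is about 5-11%. If completion did not vary by physician there would be no inflation.

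It would be wrong to read this as undermining Aim 3 as a whole, since its main interest is patient-level social risk. It has no bearing on the Aim 2 primary outcome, and Aim 3 is an exploratory chart review.

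**What to change.** Add one sentence to the Aim 3 analysis: standard errors will be clustered on the physician seen at dose one, with a small-sample correction, and the physician- and clinic-level odds ratios will be reported from that model. The correction matters, because uncorrected clustered errors still left about 5-8% in the simulations.

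GEE is an alternative. So is the Aim 2 random intercept if it converges, but it was not simulated here and may be unstable: at N=300 with 27 attendings and 78 residents, residents average only 300 × 2/(27×9 + 78×2) = 1.5 patients each.

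State also that the clinic contrast remains confounded with receipt of VR training. With two clinics, no variance adjustment removes that.

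No new data should be needed, since the dose-one physician must be identified to code resident/attending status and provider sex. The cost is slightly wider intervals for those three factors.
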